## Abstract

The rising prevalence of chronic illnesses threatens the sustainability of the healthcare system, especially due to the high cost of frequent hospitalizations. Effective self-management of chronic disease can reduce the need for urgent care but helping patients to master complex decision-making and to implement lifestyle changes is difficult. Telemonitoring systems are a promising adjunct in this regard. Such systems allow patients to monitor their physiological state (e.g. weight, blood pressure) and to receive both automated and real-time feedback from health care providers. Current systems tend to be inconvenient and costly to implement in existing clinical settings and are often limited to the monitoring of one chronic condition. We believe that delivering telemonitoring through a mobile phone will enable patients with complex chronic conditions to track their health, receive automated feedback relevant to their unique situations, and improve communication with their health care team in a cost effective and intuitive way.

In order to test the effectiveness of the intervention, we propose a 6-month randomized controlled trial of 146 patients. The study will include patients with a diagnosis of any of the following conditions or combinations of these conditions: heart failure, chronic obstructive pulmonary disease, chronic kidney disease, and/or uncontrolled hypertension. Insulin-requiring diabetes will be included as a co-morbidity to be supported by the telemonitoring application if the patient also has at least one of the four above chronic conditions. Patients will be assigned to either (1) the control group receiving usual care, or (2) the group using the mobile telemonitoring system in addition to usual care. We hypothesize that our mobile intervention will be a cost-effective and scalable tool that will improve health outcomes and quality of care, while empowering and reassuring patients and their family.

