## **Patient Population**

### ***Inclusion Criteria***

Patients who meet the following criteria will be considered for inclusion in the study:

- Adults (age 18 years or older)
- Diagnosed with HF, COPD, CKD, insulin-requiring diabetes and/or uncontrolled hypertension
- Followed by at least one of the following physicians:
  - Followed by a cardiologist at the Heart Function Clinic, University Health Network, who has primary responsibility for management of the patient's HF
  - Followed by a respirologist at the Asthma and Airway Centre, University Health Network, who has primary responsibility for management of the patient's COPD
  - Followed by [name] or another hypertension specialist at the Mount Sinai Hospital, who has primary responsibility for management of the patient's CKD and/or hypertension
  - Followed by an endocrinologist at the Endocrinology Clinic at UHN, such as [name].
- Patients with HF as the primary chronic disease:
  - Patients with HF with reduced ejection fraction (EF<0.40)
- Patients with COPD as the primary chronic disease:
  - Spirometrically confirmed diagnosis of COPD of GOLD Stage II or higher (defined as post-bronchodilator FEV1 < 80% predicted and FEV1/FVC ratio < 70%) and,
  - smoking history of  $\geq$  20 pack-years or homozygous alpha-1 antitrypsin deficiency and,
  - Prescribed an action plan for the early self-treatment of acute exacerbations
- Patients with CKD as the primary chronic disease:
  - Grade 3-5 (eGFR < 60mL/1.73 m^2)
- Patients with uncontrolled hypertension as the primary chronic disease:
  - For non-diabetics: blood pressure  $\geq$ =140/90 mmHg auscultatory (manual measurement) or  $\geq$ =135/85 mmHg oscillometric (automated measurement)
  - For diabetics: blood pressure  $\geq$ =130/80 mmHg
- Patient or their caregiver speaks and reads English adequately to provide informed consent and understand the text prompts in the application.
- Ability to comply with using the telemonitoring system (e.g, able to stand on the weight scale, able to answer symptom questions, etc.).

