### ***Exclusion Criteria***

Patients will be excluded from participating in the pilot study for any of the following reasons:

- Patients on mechanical circulatory support
- Patients on the heart transplant list
- Terminal diagnosis with life expectancy < 1 year
- Dementia or uncontrolled psychiatric illness
- Resident of a long term care facility

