### **Patient Recruitment**

Patients will be recruited during regularly scheduled visits to the UHN and Mount Sinai Hospital clinics associated with their chronic illnesses. After the clinician determines that the patient is eligible for recruitment, he/she will ask the patient if they are willing to speak to the study coordinator regarding the study. All eligible participants, based on the inclusion/exclusion criteria above, will be asked to sign a written consent form prior to being enrolled in the study (Appendix 1).

An additional recruitment strategy to asking patients if they are interested in participating in the study during their regularly scheduled clinic visit may be employed to speed up patient enrolment. This recruitment strategy has previously been used with great success for a completed and a current study at the University Health Network by [name] (co-investigator) at the Renal Clinic. It involves identifying interested patients prior to their clinic visit. The research study coordinator, an independent third party who is not part of the clinical care team, will generate an eligible patient mail out list. This list will be derived from the general clinic roster at the Hypertension Clinic (Mount Sinai Hospital) and at the Heart Function Clinic (UHN); the list will be screened and verified by the clinic nurses/physicians to ensure appropriateness (as determined by the study inclusion criteria) for mailing out invitations about the study. A separate REB amendment will be sent to the Mount Sinai Hospital REB. The mail out study invitation will be used in order to determine interest of patients who are not scheduled for an upcoming clinic visit at UHN. After identifying eligible patients, the research coordinator will mail out an invitation letter including a study description and consent form along with a pre-addressed and stamped envelope to return the signed consent form to the clinic (see Appendix 2). This will be mailed only to potential participants who have been reviewed by the clinic staff as “appropriate to be approached”. The letter will be mailed to the potential participants on behalf [name] for the Hypertension Clinic patients at Mount Sinai Hospital and [name] for the Heart Function Clinic patients at the University Health Network. Each will sign the letter as they are the clinician leads in the respective clinics. The patients will also be provided with the

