coordinator's phone number in case they require additional information or want to discuss aspects of the study, as well as to indicate interest in the study. For those who did not respond to the letter within two weeks of mailing, the study coordinator will contact them over the phone to explain the study and determine interest in participating. For all those interested in participating, the study coordinator will arrange a date and time to meet in the clinic. Details of the study and the consent form will be reviewed in-person at this time to ensure that patients are fully informed about all aspects of the study and are freely providing their consent to participate.

To perform a sample size calculation, the primary outcome measure SF-36 was used. Assuming a moderate effect size on the general health dimension of the SF-36 of 10.5 points (39), a score of 57 +/- 21 for the control group (40), 80% power, and alpha=0.05 (two-sided), the sample size per group was calculated to be 63 (<http://clincalc.com/Stats/SampleSize.aspx>). Assuming 15% of patients will be lost to follow-up (including mortality) (36, 37), the sample size per group is 73. Hence 146 patients will be enrolled during the trial and randomized 1:1 into control and telemonitoring groups.

To perform the randomization, the online computer generated randomization tool, Research Randomizer, will be used ([www.randomizer.org](http://www.randomizer.org)). The study coordinator performing the recruitment will be blinded until the patient has consented to participate. The participants will be blocked randomized (blocks of 4) and stratified into groups according to their primary condition (HF, COPD, hypertension, insulin-requiring diabetes, and CKD). The HF group will further be stratified based on NYHA classification (NYHA class 2-3, NYHA class 4), and the hypertensive patients will be stratified to those with and those without diabetes.

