**Data Analysis:** Post-trial data and change scores will be compared between the control and intervention groups using independent Student t tests and Mann-Whitney tests (for normally and not normally distributed data, respectively). Paired Student t tests and Wilcoxon signed rank tests will be performed to compare baseline and post-study data within the control and telemonitoring groups. The statistical analyses will be performed using the statistical software application SPSS (IBM Corporation, USA). The cost evaluation will be performed by comparing any savings through reductions in hospitalization, emergency and clinic visits, through the use of the intervention. This will further include amortizing the equipment costs and factoring in additional clinical, technical, and management resources. An analysis of indirect costs will also be performed, such as days absent from work. Interview data will be analyzed using a conventional content analysis approach (49). Two researchers will analyze the transcripts independently and code the transcripts with the software program NVivo (QSR International, Doncaster, Victoria, Australia).

The Principle Investigator will keep all study data in a secure and confidential location for 10 years after the completion of the study and then they will destroyed by shredding of paper or erasing of digital information. All participants will be assigned a unique identifier, which will replace any identifiable information contained in the research data. A list linking the study number with the participants' name will be kept by the Principle Investigator in a secure place in a locked cabinet.

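### Do the missing NYHA class 1 stratum and the mixed wording on insulin-requiring diabetes undermine eligibility or randomization?

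*Combined protocol and SAP*

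**What the plan says.** **Heart failure strata.** Patient Recruitment sets blocks of 4, with participants "stratified into groups according to their primary condition (HF, COPD, hypertension, insulin-requiring diabetes, and CKD". It then subdivides two of these conditions. Hypertension is split by diabetes status, and for heart failure: "The HF group will further be stratified based on NYHA classification (NYHA class 2-3, NYHA class 4". For heart failure as the primary disease, the Inclusion Criteria set one specific requirement, "Patients with HF with reduced ejection fraction (EF<0.40", and no functional class. None of the five Exclusion Criteria mentions NYHA class.

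**Diabetes.** The Abstract describes the qualifying conditions this way: "diagnosis of any of the following conditions or combinations of these conditions: heart failure, chronic obstructive pulmonary disease, chronic kidney disease, and/or uncontrolled hypertension". On diabetes it adds: "Insulin-requiring diabetes will be included as a co-morbidity to be supported by the telemonitoring application if the patient also has at least one", meaning one from that list. The Inclusion Criteria instead name insulin-requiring diabetes among five diagnoses joined by and/or, and accept follow-up by an endocrinologist as a qualifying route. Objectives lists diabetes together with the other four conditions. Outcome Measures gives it its own outcome, HgbA1c. However, the Inclusion Criteria contain separate primary-disease requirements for heart failure, COPD, CKD and hypertension only.

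**The concern.** A stratified randomization should provide a list for every patient who can be enrolled. As written, a class 1 patient with a low enough ejection fraction can pass screening and sign consent, and only then be found to have no list. Staff must choose a list or turn the patient away, and the plan does not say which.

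On diabetes, a patient with that condition alone is out according to the Abstract and in according to the Inclusion Criteria. Two coordinators reading different pages could decide differently. Diabetes is also a primary condition for randomization without a primary-disease block of its own.

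If these gaps let staff influence allocation, disturbed the arm sizes or left the analysed population undefined, the primary SF-36 comparison would be at risk.

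**Working it through.** **1. The plan's sample size.** Inputs from Patient Recruitment: difference 10.5, SD 21, 80% power, two-sided alpha 0.05, 15% loss.

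- n per arm = 2 × (1.960 + 0.842)² × 21² / 10.5² = 2 × 7.85 × 4 = 62.8, rounded up to 63, as stated.
- 63 × 1.15 = 72.45, rounded up to 73; 2 × 73 = 146, as stated. (Dividing instead, 63 / 0.85 = 74.1, gives 75 per arm. That is a separate matter and has nothing to do with strata.)

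No stratum, NYHA class or diabetes share enters the calculation, so neither gap can alter N.

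**2. The lists.** Heart failure 2 + COPD 1 + hypertension 2 + diabetes 1 + CKD 1 = 7. None names class 1.

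**3. What can happen to a class 1 patient.**

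| Handling | Lists | Consequence |
|---|---|---|
| Placed on the class 2-3 list | 7 | Next assignment in the same sequence, identical to a list labelled 1-3 |
| Placed on the class 4 list | 7 | Still assigned at random, 1:1; NYHA balance within heart failure slightly looser |
| Not enrolled | 7 | Lost before randomization, so the comparison is untouched |
| Given a new list | 8 | Finer stratification, one more unfinished block |

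The first row is the natural choice, and it is also what a relabelling would produce, so the relabelling gains nothing in balance. With 2 patients per arm in each block of 4, the arms can differ by at most 2 within an unfinished block. The worst case over all lists is 7 × 2 = 14 with or without the relabelling, and 8 × 2 = 16 with a separate class 1 list.

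Validity rests on each patient being assigned at random, whichever list is used. The planned comparison, "Post-trial data and change scores will be compared between the control and intervention groups using independent Student t tests and Mann-Whitney tests", has no stratum term, so the list label does not enter the test either. That is a separate fact: it is not what protects N or the 1:1 ratio.

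**4. Diabetes, section by section.**

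| Section | Role of insulin-requiring diabetes |
|---|---|
| Abstract | Only alongside one of four conditions |
| Objectives | Listed with the other four |
| Inclusion Criteria | One of five diagnoses; endocrinology route; no primary-disease block |
| Patient Recruitment | One of five primary conditions |
| Outcome Measures | Own outcome, HgbA1c |

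Primary conditions 5, primary-disease blocks 4, so 5 − 4 = 1 without a block. For a patient who has diabetes plus another listed condition, the sections agree. They part only for diabetes alone. There, Patient Recruitment says which text governs consent: "All eligible participants, based on the inclusion/exclusion criteria above, will be asked to sign a written consent form". Recruiters therefore work from the Inclusion Criteria, not the Abstract. A diabetes-only patient who enters has a list, a glucose meter (Methods), a disease-specific outcome and the common SF-36 endpoint.

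**5. Numbers affected.** Not derivable: the documents give no NYHA distribution and no shares by primary condition.

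**The case for a change.** The best case for acting is that eligibility and stratum assignment should be rules that any two coordinators apply in the same way, and here they are not. Screening never asks for NYHA class, so the gap may appear only after consent. The high-risk description in Background might explain why class 1 was left out, but it is not an eligibility criterion. Block size is fixed at 4, so freedom to choose between two lists is undesirable in principle. Relabelling would need no new data, since NYHA class is already required for stratification and for the heart failure prognostic score.

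The textual facts stand, and so does the point about undocumented discretion. The consequences do not follow. Nothing in the documents shows that upcoming assignments are visible to whoever picks the list, so no allocation bias can be asserted. Looser balance would require placing class 1 patients on the class 4 list, which nothing suggests. It also goes too far to say that diabetes has no disease-specific entry requirement. The diagnosis is restricted to the insulin-requiring form, and endocrinology follow-up is a named route; only the separate block is absent.

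Nor is the correction entirely cheap. An amendment needs ethics review. Reconciling the diabetes wording means that the sponsor must choose a reading. If the co-morbidity rule were kept and the diabetes list dropped, 7 − 1 = 6 lists would remain, and any diabetes-only patients already enrolled would have to be dealt with.

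**Conclusion.** No change to the plan follows. The NYHA point is a labelling gap that staff would fill sensibly. The diabetes point is an abstract that does not match the body of the protocol, together with one missing sub-heading in the criteria. The demonstrated effect on N (146), the allocation ratio, arm balance and the validity of the SF-36 comparison is nil, and the number of patients concerned is unknown.

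This rests on three assumptions: class 1 patients go on the lower heart failure list or are not randomized; recruiters apply the Inclusion Criteria, as Patient Recruitment directs; and upcoming assignments are not known when the list is chosen. The sections could be brought into line if the protocol is reopened for another reason. Which reading of the diabetes rule was intended is for the sponsor to say. The trial report should describe the patients actually enrolled, by primary condition and NYHA class, whichever reading was used.

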## **Telemonitoring Technology**

*Medly* will enable patients with complex chronic illnesses, including MCCs, to take clinically relevant physiological measurements with wireless home medical

devices and to answer symptom questions on the mobile phone. The measurements will be automatically and wirelessly transmitted to the mobile phone and then to a data server. Specifically, patients with HF will monitor daily weight and blood pressure/heart rate, CKD patients will monitor blood pressure, diabetes patients will monitor blood glucose and HF, COPD, and CKD patients will monitor symptoms. Hypertension patients will monitor their blood pressure. Automated self-care instructions/messages that have been carefully developed with healthcare specialists will be sent to the patient based on the readings and reported symptoms. If there are signs of their status deteriorating, an alert will be sent to a clinician that is responsible for the particular chronic condition of concern (i.e., in the specific specialty clinic). The clinicians will have all the relevant patient data sent to them and will be able to access (through a secure web portal) to view historical and trending data for their patients. Additional app features will also be available, such as educational videos for proper inhaler use for COPD patients.

## **Methods**

The control group will receive usual care, and the intervention group will receive usual care plus the telemonitoring intervention. Both groups will be followed for 6 months. Study data collection will occur during regularly scheduled visits, no additional study visits beyond what patients experience in usual care, it is anticipated that patients will be recruited, randomized, and trained during a routine scheduled clinics. If this proves inconvenient for the patient, an additional study visit may be scheduled at their convenience. Similarly, we anticipate collecting the study equipment and administer the follow up questionnaire at a regularly scheduled visit. Each intervention study participant will be provided with a smartphone. This phone will be loaded with the application and a limited data plan to enable data transfer. Patients will also be provided with relevant home medical monitoring devices (e.g., weight scales and blood pressure monitors for HF patients, blood pressure monitors for CKD and hypertension patients, and blood glucose meters for diabetes patients). Patients will be asked to take measurements and record symptoms at a specified frequency at their homes. Home measurement depends on the specific chronic condition(s). HF, COPD, and diabetes are generally monitored daily whereas hypertension and CKD are generally monitored several times per week as specified by the algorithm developed in conjunction with specialists. Patients will be notified when they should take at home measurement through the application. The research team, as informed by the patient's clinician(s), will enter patient-specific baseline information into the telemonitoring system dashboard, such as individual target weight ranges, target blood pressure ranges, medication lists, COPD action plan, etc.

## **Outcome Measures:**

The primary outcome will be health status as measured with SF-36 because this metric will be relevant to all chronic conditions under investigation. A secondary

outcome measure will be the cost (from the health system and patient perspectives). The cost of healthcare will include hospitalizations, emergency department (ED) visits, clinic visits, delay of hemodialysis commencement, medications, and telemonitoring program, as relevant to the different chronic illnesses and will include disease-specific sub-analyses.

Other secondary outcome measures will include combined hospitalization for any reason or death from any cause within 6-months after enrolment, hospitalization, mortality, days in hospital, number of emergency department (ED) and clinic visits, and medications. Secondary outcome measures will also include general quality of life as measure by the EuroQol 5D-RL, anxiety and depression as measure with the Hospital Anxiety and Depression Scale (41) and patients' self-efficacy to self-manage their disease as measured with the Self-Efficacy for Managing Chronic Disease Scale (42) (Appendix 3).

Disease specific outcome measures will include:

- HF
  - left ventricular ejection fraction (LVEF)
  - brain natriuretic peptide (BNP)
  - self-care as measured by the Self-Care of Heart Failure Index (43) (Appendix 4)
  - Heart-failure specific quality of life as measured by Minnesota Living with Heart Failure Questionnaire (44) (Appendix 4)
  - Shortness of breath as measure using a visual analogue scale (VAS) for dyspnea (Appendix 4)
  - Blood work: creatinine, sodium, potassium, hemoglobin, urate
  - Prognostic score as determined by the Seattle Health Failure Model (requires: age, gender, NYHA class, weight, ejection fraction, systolic BP, medication list (including diuretics), lab results (hemoglobin, lymphocytes, uric acid, total cholesterol, sodium) and QRS interval)
- COPD
  - forced expiratory volume in one second (FEV1)
  - symptoms score from the telemonitoring system
  - COPD Assessment Test (CAT) score (45) (Appendix 5)
  - COPD-specific knowledge after 6-months of application usage, as measured by the Bristol COPD Knowledge Questionnaire (BCKQ)(46) (Appendix 5)
  - patient self-efficacy at 6 months as measured by the COPD Self-Efficacy Scale (CSES)(47) (Appendix 5)
  - COPD severity as measured by the BODE Index(48) at 6 months (Appendix 5)

- CKD
  - estimated glomerular filtration rate (eGFR)
  - symptoms score from the telemonitoring system
  - blood pressure as measured by an automatic blood pressure monitor
- Hypertension
  - blood pressure as measured by an automatic blood pressure monitor
  - average 7-day blood pressure
- Diabetes
  - HgbA1c

**Data Acquisition:** Number of hospitalizations, days in hospital, number of ED and clinic visits, and medications will be determined through the hospital EMR and a manual chart review of all participants' clinical records. Combined hospitalization will be verified by patient participants through self-report with the help of a questionnaire. The cost of the intervention will be tracked, including for equipment costs and human resources for clinical support, technical support, and program management. Standard cost values for a day in-hospital, ED visit, etc. will be used to estimate net cost savings or expenditures. Values for pre- and post-trial health outcome measures (eg, blood test results) will be obtained through hospital clinical records or through the *Medly* database for symptoms. Pre- and follow up questionnaires (baseline, 1-month, and 6-months), will be administered to both control and intervention groups that contain the validated survey tools listed above. Participants will be able to complete the questionnaires at the clinic or complete it at home. Participants that chose to complete the questionnaire at home will be given a pre-paid self-addressed envelope to mail the questionnaire back to the study team. The 1-month questionnaire will be given to participants upon enrolment with instructions to complete the questionnaire one month after starting the trial and to mail it back to the study team using the pre-paid envelope. The study coordinator will call each participant at the 1-month period to remind participants to complete the questionnaire. In addition to the baseline and follow up questionnaires that are applicable to all patient participants (Appendix 3), patients with HF and/or COPD will also receive the validated survey tools listed above (Appendix 4 and 5). Average 7-day blood pressure will also be recorded from patients with a primary diagnosis of hypertension during their first week in the study (baseline) and their last week in the study (6-months). To do this, patients will be provided with a digital blood pressure monitor which they will use to take blood pressure 4 times per day (2 times in the morning and 2 times in the evening) over each 7-day period. Patients will return the blood pressure monitor to the study team who will download the

data and calculate the average 7-day blood pressure value. Usage data, in terms adherence to taking measurements and use of the different features, will also be data-mined from the servers.

In addition to the quantitative metrics, all participants will be asked basic questions such as their self-care practice and their thoughts on remote patient monitoring at the start of the study. A subgroup of the intervention arm will also be interviewed individually to assess their experiences and perceptions regarding the use of *Medly* at the end of the study. The number of patients that will be interviewed will depend on when saturation of information is reached, typically 15-20 participants. The interviews will be conducted in a quiet and private space within a clinic (e.g., consultation room or education room). Prior to the interview, participants will be informed that notes will be taken and they will be audio taped for data analysis. See Appendix 6 for sample patient interview questions. The clinicians involved in the trial will also be asked to participate (see Appendix 7 for clinician consent form) in interviews to determine their perceptions of *Medly*. See Appendix 8 for sample clinician interview questions.

All study data will be kept for 10 years after the completion of the study and then destroyed by shredding of paper or erasing of digital information.

**Data Analysis:** Post-trial data and change scores will be compared between the control and intervention groups using independent Student t tests and Mann-Whitney tests (for normally and not normally distributed data, respectively). Paired Student t tests and Wilcoxon signed rank tests will be performed to compare baseline and post-study data within the control and telemonitoring groups. The statistical analyses will be performed using the statistical software application SPSS (IBM Corporation, USA). The cost evaluation will be performed by comparing any savings through reductions in hospitalization, emergency and clinic visits, through the use of the intervention. This will further include amortizing the equipment costs and factoring in additional clinical, technical, and management resources. An analysis of indirect costs will also be performed, such as days absent from work. Interview data will be analyzed using a conventional content analysis approach (49). Two researchers will analyze the transcripts independently and code the transcripts with the software program NVivo (QSR International, Doncaster, Victoria, Australia).

The Principle Investigator will keep all study data in a secure and confidential location for 10 years after the completion of the study and then they will destroyed by shredding of paper or erasing of digital information. All participants will be assigned a unique identifier, which will replace any identifiable information contained in the research data. A list linking the study number with the participants' name will be kept by the Principle Investigator in a secure place in a locked cabinet.

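### Hospital days, admissions and visit counts are compared between arms without regard to time alive, which slightly favours the arm with more deaths

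*Combined protocol and SAP*

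**What the plan says.** Under Outcome Measures, the secondary outcomes include "combined hospitalization for any reason or death from any cause within 6-months after enrolment, hospitalization, mortality, days in hospital" and the "number of emergency department (ED) and clinic visits, and medications". 

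The Data Analysis paragraph gives one between-arm rule for all quantitative outcomes: "Post-trial data and change scores will be compared between the control and intervention groups". The tests that it names for this purpose are "independent Student t tests and Mann-Whitney tests (for normally and not normally distributed data, respectively". The only other tests named are within-arm: "Paired Student t tests and Wilcoxon signed rank tests will be performed to compare baseline and post-study data". No method is named for binary, count or time-to-event outcomes. There is no person-time offset, no censoring rule, and no statement of how a patient who dies is counted. The same paragraph bases the cost evaluation on savings from fewer admissions, ED visits and clinic visits.

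Follow-up is fixed in Methods: "Both groups will be followed for 6 months". The sample size text under Patient Recruitment expects it to be incomplete: "Assuming 15% of patients will be lost to follow-up (including mortality". Under Data Acquisition, admissions, hospital days and visits come from the hospital's electronic record and a review of every participant's chart. No source is named for deaths.

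**The concern.** A patient who dies in month 2 can accrue hospital days and visits for two months only. A t test or Mann-Whitney test on the six-month total reads the low total as a good result. If mortality differs between arms while the rate of use among the living does not, the comparison of totals leans towards the arm with more deaths. The same holds, more weakly, for hospitalization taken alone.

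Health service use and cost are both named in the central research question. In the cost evaluation, use that stopped because the patient died would appear as a reduction obtained with the intervention.

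The composite of hospitalization or death has a different weakness. The named tests give no risk difference, risk ratio or hazard ratio, and they cannot use event times or censor a patient who leaves early.

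**Working it through.** **The plan's own figures.** SF-36 sample size: n = 2 × (1.96 + 0.84)² × 21² / 10.5² = 62.7, so 63 per group, as stated. The allowance for loss reproduces as 63 × 1.15 = 72.45, so 73 per group and 146 in all. Fifteen percent of 146 is about 22 patients. The plan does not split these into deaths and other losses, or by arm, and gives no power for the outcomes discussed here.

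**Assumed inputs** (the documents give none): deaths 10% vs 5%, uniform over 180 days and unrelated to use; 0.004 admissions per day alive in both arms; mean stay 8 days.

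**Time alive.** Mean = 180 × (1 − p/2).
- 10% deaths: 180 × 0.95 = 171.0 days
- 5% deaths: 180 × 0.975 = 175.5 days

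**Hospital days.** Rate × stay × time alive, with 0.004 × 8 = 0.032.
- 171.0 × 0.032 = 5.47
- 175.5 × 0.032 = 5.62

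This ignores that a stay is cut off at death or day 180 and that no new admission starts during a stay. Simulation with both features gives about 5.0 to 5.1 vs 5.2. Either way the gap is 0.1 to 0.2 day, in favour of the arm with twice the deaths.

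**Days alive and out of hospital.** From the formulas: 171.0 − 5.47 = 165.5 and 175.5 − 5.62 = 169.9. Simulation gives 166 vs 170. The arm with fewer deaths is now ahead by about 4 days.

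**Per unit time alive.** Admissions per 180 days alive are 0.70 in both arms in the simulation, so the gap in raw totals is due to time at risk alone.

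**Range.** For any rate that is equal in both arms, the ratio of raw means is approximately (1 − p₁/2) / (1 − p₀/2):

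| Deaths | Ratio | Shortfall in high-death arm |
|---|---|---|
| 10% vs 5% | 0.950/0.975 = 0.974 | 2.6% |
| 15% vs 5% | 0.925/0.975 = 0.949 | 5.1% |
| 15% vs 0% | 0.925/1 = 0.925 | 7.5% |
| 30% vs 0% | 0.850/1 = 0.850 | 15% |

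The last row is the extreme that the 15% allowance permits: all 22 losses are deaths, all in one arm (22/73 = 30%). At 15% vs 5%, the formula gives hospital days of 5.76 × 0.925 = 5.33 vs 5.76 × 0.975 = 5.62, a gap of 0.3 day.

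**Effect on the tests at 73 per arm.** For hospital days at 10% vs 5% deaths, the high-death arm has the lower mean in about 53 to 54% of simulated trials. A significant result in its favour occurs in 3.1 to 3.7% (t or Mann-Whitney), against a nominal 2.5%. In a second illustration, with a mean of 2 visits per 6 months alive varying between patients, Mann-Whitney on visit counts significantly favours the high-death arm in 4.4% of trials at 15% vs 5% deaths and 13.5% at 30% vs 0%.

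**Hospitalization-or-death.** Probability = 1 − (1 − p) × exp(−0.004 × 180), with exp(−0.72) = 0.487.
- 10% deaths: 1 − 0.90 × 0.487 = 56%
- 5% deaths: 1 − 0.95 × 0.487 = 54%

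The arm with more deaths looks worse, as it should. For a fully observed yes/no outcome the p-values nearly agree: at 22/73 vs 36/73, t gives 0.0178, Mann-Whitney 0.0183 and chi-square 0.0179.

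**Effect size.** As a separate assumption, at 0.002 admissions per day 1 − exp(−0.36) = 30% are ever admitted. The median number of hospital days is then 0 in both arms, and a Mann-Whitney p-value with medians says nothing about size.

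**The case against.** The case for leaving the plan alone is that the bias is small, the outcomes are secondary, and mortality is itself a listed outcome, so readers would see an excess of deaths beside the hospital days. A gap of 0.1 to 0.2 day is far below the standard error of the difference, about 1.4 to 1.6 days. This stands as a limit on the size. It does not justify a comparison known to lean one way when the correction is cheap, and a separate mortality line does not correct the utilization or cost figures.

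A payer may also say that care not delivered after death is truly not paid for. That is fair for total spending, but the plan presents the difference as savings through the intervention, and that needs survival beside it.

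Three stronger readings are tempting, and the documents do not support them.

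- A reader might infer that hospitalization-or-death can also favour the arm with more deaths. Death is an event in that composite, so more deaths raise it.
- A reader might infer that 15% of utilization data will be missing. The 15% is an allowance for the SF-36 sample size. Review of every participant's records limits loss among the living, including those who stop returning questionnaires. It cannot restore time at risk after death.
- A reader might infer that the direction of the bias is certain. It follows only if use while alive is unrelated to death. If patients are heavily hospitalized before they die, the bias could shrink or reverse.

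The remedy has limits too. An offset corrects for exposure time but not for informative death, so rate ratios must be read beside mortality. Days alive and out of hospital is an added outcome and should not silently replace the prespecified one.

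**Conclusion.** The point holds for days in hospital, admissions, and ED and clinic visits, and through them for the cost comparison. The named tests ignore time alive. With equal rates while alive, the arm with more deaths shows totals about 3% lower at 10% vs 5% deaths and about 5% lower at 15% vs 5%; for hospital days this is 0.1 to 0.3 day. These sizes rest on assumed mortality, admission rate and stay, and on deaths unrelated to use.

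For hospitalization-or-death the point is narrower: the tests give nearly the same p-value as a chi-square test when follow-up is complete, but no suitable effect size and no use of event times or censoring.

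The primary SF-36 analysis and the sample size are not touched. This is a modest weakness in secondary analyses that is worth correcting before the data are analysed.

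**What to change.** Add to the Data Analysis paragraph:

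1. Admissions, ED visits and clinic visits: negative binomial regression with log time alive and observed as offset, reported as a rate ratio with 95% CI and read alongside mortality by arm.
2. Days in hospital: keep as prespecified, and add days alive and out of hospital over 180 days as the between-arm comparison that accounts for death. Document it as an addition.
3. Hospitalization-or-death: time to first event by log-rank test and Cox model, with a hazard ratio and 95% CI, censored at last chart contact. Stratify by primary condition only. The full randomization scheme has seven strata (HF 2, COPD 1, hypertension 2, diabetes 1, CKD 1), and 146/7 is about 21 patients, or roughly 10 per arm, per stratum.
4. Cost: state how time after death is treated, and report the cost difference beside mortality.

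The cost is some extra programming. Admission and death dates must be abstracted during the chart review already planned, and a source for deaths must be named, since the Data Acquisition paragraph gives none and deceased patients cannot verify events by self-report. Sample size, visits and patient contact do not change.
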